## **2 Study Objectives**

### **2.1 Primary Objective**

The primary objective of this study is to assess the safety of a 2-dose vaccination schedule of mRNA-1325 Zika vaccine, given 28 days apart, across a range of dose levels in flavivirus-seronegative and flavivirus-seropositive subjects compared with placebo.

### **2.2 Secondary Objective**

The secondary objective of this study is to assess the immunogenicity of a range of doses of mRNA-1325 Zika vaccine and to select a dose for further development, based on changes from Baseline in the following tests:

- ZikaV-specific neutralizing antibody titers measured by a Plaque Reduction Neutralizing Titer EC50 (PRNT50);

### **2.3 Exploratory Objective**

The exploratory objectives of this study are to:

- Assess the impact of mRNA-1325 Zika vaccine on a range of other functional and diagnostic flavivirus assays.
- Assess ZikaV antigen-specific stimulation of T cells measured by interferon gamma (IFN $\gamma$ ) enzyme-linked ImmunoSpot (ELISPOT) on subject-derived peripheral blood mononuclear cells (PBMCs), if results of interim immunogenicity analyses warrant further analyses of samples .

### 3 Investigational Plan

#### 3.1 Study Design

This is a Phase 1, double-blind, placebo-controlled, dose-finding study to evaluate the safety and immunogenicity of a range of dose levels of mRNA-1325 Zika vaccine given in a 2-dose vaccination schedule, 28 days apart, and compared with placebo in healthy adult subjects (18 to 49 years of age, inclusive). mRNA-1325 is an mRNA-based vaccine candidate being tested for its ability to safely induce an immune response able to prevent ZikaV infection.

ZikaV is a single-stranded RNA flavivirus, which is transmitted to humans by a mosquito vector (mainly *Aedes aegypti* but other *Aedes* mosquitoes are believed to be competent vectors) or by person-to-person spread, mainly through sexual transmission. Currently there is no vaccine to protect against this disease, which has spread rapidly from Asia to most tropical and subtropical regions including the Americas.

This is a 2-part study. Part A includes dose-finding, safety, and immune testing through 28 days following the second vaccination. Once subjects complete the final visit in Part A, they will be entered into Part B. Part B is a blinded follow-up period with assessment of safety through 12 months and immune persistence at 168 ( $\pm 15$ ) days and 364 (+15) days following the second vaccination in Part A. Immune persistence at 168 days and 364 days will be evaluated if interim immunogenicity analyses warrants long term analyses of persistence.

#### **Part A**

Subjects will be randomly assigned in a blinded fashion in an approximate 4:1 ratio to receive mRNA-1325 or placebo at 1 of 3 dose levels (10  $\mu\text{g}$ , 25  $\mu\text{g}$ , or 100  $\mu\text{g}$ ), with each subject receiving 2 vaccinations separated by 28 (+7) days. Dosing will begin with 10  $\mu\text{g}$  (Cohort 2), followed by 25  $\mu\text{g}$  (Cohort 3), and then 100  $\mu\text{g}$  (Cohort 4). There will be no Cohort 1 included in this study. Approximately two-thirds of the enrolled subjects at each dose level will be flavivirus naïve and approximately one-third will be flavivirus seropositive as a result of having received a yellow fever vaccination in the past 20 years by either: a) military assignment in the previous 20 years that requires a yellow fever vaccination; or 2) yellow fever vaccination documented on an international certificate or other confirmatory documentation of yellow fever vaccination.

Cohort and treatment assignment are shown in [Figure 3-1](#).

**Figure 3-1 Cohort and Treatment Assignment**

[figure not shown]
Cohort	Flavivirus Status	Treatment Assignment (µg mRNA-1325 or placebo)	Total (Ratio)
2	+	10	30 (4:1)
	-	10	
	+	placebo	
	-	placebo	
3	+	25	30 (4:1)
	-	25	
	+	placebo	
	-	placebo	
4	+	100	30 (4:1)
	-	100	
	+	placebo	
	-	placebo	

Abbreviations: +, flavivirus seropositive; -, flavivirus seronegative.

For each cohort, a sentinel safety group will occur with 3 flavivirus-seronegative subjects randomized to mRNA-1325 and followed for 7 days after first vaccination, with review of reactogenicity and safety laboratory results, prior to randomizing the remainder of the cohort. An IST will oversee the safety of the trial and will review blinded safety data during Part A of the study to ensure adherence to the protocol, monitor safety laboratory test results and reactogenicity, and raise concerns to the SMC should there be safety issues or operational challenges that could affect subject safety. Only after review by the IST of the blinded safety data (reactogenicity, safety labs, and AEs) through 7 days following first vaccination of the sentinel safety lead-in for each cohort planned will approval be given to allow randomization of the remainder of that cohort. The SMC will approve escalation to the next higher dosing cohort after review of blinded safety data of the currently dosed cohort through 7 days following the second vaccination and any cumulative safety data of all cohorts as the trial advances. The SMC will also be convened (ad hoc meeting) if a pause rule is triggered.

A diagram of the dosing schema by cohort is shown in [Figure 3-2](#).

**Figure 3-2 Dosing Schema by Cohort**

Abbreviations: D, day; Plc, placebo; SMC, safety monitoring committee.

Note: Yellow shading depicts safety follow-up of the first vaccination period and grey shading depicts safety follow-up of the second vaccination period for cohorts by dose sequence.

Note: The SMC will approve escalation to the next higher dosing cohort after review of blinded safety data of the currently dosed cohort through 7 days following the second vaccination and any cumulative safety data of all cohorts as the trial advances.

The vaccine will be administered as an IM injection (0.5 mL) into the deltoid muscle as a 2-dose vaccination schedule at Visits 1 and 4 (at least a 28-day interval between dosing). The second dose of study drug will be administered preferably in the same arm used for the first dose. Vaccine accountability, dose preparation, and vaccine administration will be performed by unblinded pharmacy personnel, who will not participate in any other aspect of the study. The remainder of the site staff and all subjects will remain blinded to treatment assignment.

Screening and consent will occur over a 28-day period before randomization (West Nile virus serology screen can occur up to 90 days prior to randomization). A total of 30 subjects for each dose cohort will be assigned, 24 subjects to mRNA-1325 and 6 subjects to placebo (approximate 4:1 ratio overall). The first 3 subjects for each dose level will be randomized to mRNA-1325. Subjects who meet all eligibility criteria will receive the first vaccination at Visit 1. Of note, a subject who has met all eligibility criteria but is noted to have a blood pressure, heart rate or respiratory rate that is Grade 2 or greater (even after relaxing/resting) in the clinic on the day of vaccination should not receive a vaccination on that day and will need to return on a subsequent day for their vaccination. Similarly, if a subject has a fever ( $>37.9^{\circ}\text{C}$ ) or an intercurrent illness, vaccination should be withheld until resolved (as specified in exclusion criterion 20). Each subject will be monitored in the clinic for at least 1 hour following vaccination to assess for immediate reactogenicity, with vital sign measurements and local and

systemic reactogenicity toxicity scored at that time. The highest toxicity recording will be entered into the electronic case report form (eCRF).

Subjects will be instructed on recording reactogenicity, AEs, and medications (prescription or over-the-counter) on the memory aid (ie, diary card), and will be provided measuring tools, and instructed to call or return to the clinic within 24 hours if a reactogenicity score reaches Grade 3 or greater during the first 7 days following vaccination. As standard practice, a reminder call will be made to the subject by the site at least once during the first 7 days following each vaccination to answer any questions and ensure that the memory aid is being completed correctly and consistently. All subjects will return on 7 (+3) (cellular PBMC testing) and 28 (+7) (humoral neutralization testing) days following each vaccination for safety assessments and blood sampling for immune testing.

Safety assessments will include monitoring and recording of solicited (local and systemic reactogenicity) events (first 7 days after each vaccination); clinical laboratory test results including hematology, serum chemistry, coagulation, and urinalysis; vital sign measurements; and physical examination findings (Day 7 after each vaccination) and unsolicited AEs (throughout Part A). All unsolicited AEs and concomitant medication (including over the counter) usage will be collected. Specific categories of safety data collected will include SAEs, AEs of special interest (AESIs), AEs leading to study withdrawal, and medically attended AEs. At clinic visits, the investigator will review, confirm, and grade the reactogenicity recorded in the memory aid and inquire about and review AEs and medications.

All safety laboratory tests will be performed according to [Table 6-1](#). Safety laboratory tests will be performed during Screening (to allow for assessment of inclusion and exclusion criteria), on the day of first vaccination (Visit 1), 7 (+3) days following each vaccination (Visit 2 and Visit 5), and 28 (+7) days following each vaccination (Visit 4 [prior to second vaccination] and Visit 7). At 17 ( $\pm$ 3) days following each vaccination (Visit 3 and Visit 6) and at 21 [+3] days after the first vaccination (Visit 3a) for the sentinel subjects, a subset of safety laboratory tests will be performed as specified in [Table 6-1](#). Blood test results (pre-vaccination) at Visit 1 will be the basis for evaluation of changes from Baseline after vaccination.

Blood samples for immunogenicity assessments (cellular and humoral) will be collected the day of vaccination (before vaccination) and 7 (+3) and 28 (+7) days, respectively, following each vaccination. Subjects that miss the second vaccination due to noncompliance with the visit schedule and not due to a cohort pause will still be required to follow the original visit

and testing schedule. These subjects will be asked to undergo blood collection to comply with a second immune test at Visit 7 (56+7 days after first vaccination).

To allow cohort advancement, the following data from the highest dosed cohort is expected to be reviewed by the SMC: 1) toxicity scoring of safety laboratory test results through 7 days following the second vaccination (through Visit 5); 2) toxicity scoring of vital signs and reactogenicity through 7 days following the first and second vaccination (through Visit 5); 3) all unsolicited AEs (with grading and relatedness). Data will be prepared by dose category and timing relative to the last vaccination. As safety data on all cohorts accumulate, the SMC also review ongoing AEs as well as cumulative safety laboratory test results, reactogenicity, and AEs across vaccine doses for subjects remaining in Part A of the study, thereby providing a cumulative and comprehensive review of safety. Should a cohort pause occur due to pre-specified criteria, the SMC will be convened for an unscheduled (ad hoc) meeting and be provided with specific safety data related to the trigger of the pause.

Part A is concluded for each subject at the time when they return to the clinic for Visit 7 (28 days following the second vaccination). At that time, a subject will be entered into Part B of the study. Once query resolution and immune testing is completed for each cohort in Part A, the database will be locked. Results will be provided to the Sponsor, SMC, and IST. The Sponsor may determine whether dosing adjustments are required during the conduct of the study based on either safety or immune responses per cohort. As dose escalation occurs, cumulative analyses will be included for each subsequent data lock to allow for all prior dosing cohorts to be analyzed by cohort, treatment assignment, and in aggregate for mRNA-1325 exposure. Subject-level individual treatment assignment will not be released to the subjects or to those individuals involved in managing or assessing safety in Part B of the study until that portion of the study is completed.

The full schedule of events for Part A is shown in [Table 6-1](#).

### **Part B – 12 Month Follow-up After Final Vaccination**

To monitor for longer-term safety and immune persistence, each subject will be entered into a continued, blinded follow-up period (Part B). This period will be conducted such that subjects, observers, and safety monitors will remain blinded to treatment assignment. Part B of the study is initiated for a subject once they have returned for Visit 7 (28 days following the second vaccination). The safety database utilized for Part B may be accessed by the pharmacovigilance

safety team for safety signal detection at scheduled intervals for ongoing assessments for a given vaccine candidate as well as for the mRNA platform technology.

Once entered into Part B, each safety contact will occur by telemedicine (eg, telephone, text message, internet) every 28 ( $\pm 7$ ) days, and blood samples for immune persistence will be collected from each subject at 168 ( $\pm 15$ ) days and 364 (+15) days following the second vaccination. Immune persistence at 168 days and 364 days will be evaluated if interim immunogenicity analyses warrants long term analyses of persistence. Each safety contact will capture outcomes of any AESI or SAE that remains unresolved since the last visit or is newly identified through scripted query. The telemedicine visits may require additional data through medically attended visits, in addition to and medications and vaccination taken by the subject during this time. Subjects will have consented during study enrollment to allow access to additional medical records needed to complete Part B, thereby allowing the blinding of the treatment assignment to be maintained.

The full schedule of events for Part B is shown in [Table 6-2](#).

When all subjects have completed their final contact (approximately 12 months after their last vaccination), immune testing is completed, and all queries resolved, the database will be locked and analyzed with a final clinical study report provided to regulators.

## **3.2 Selection of Study Population**

Healthy male or female subjects will be enrolled in at least 2 sites in the United States or its territories. Approximately 90 subjects are planned to be randomly assigned to receive study treatment.

### **3.2.1 Inclusion Criteria**

Each subject must meet all of the following criteria during the screening period to be enrolled in this study:

1. The subject is male or female between 18 and 49 years of age, inclusive.
2. The subject has a body mass index between 18 and 35 kg/m^2, inclusive.
3. The subject is considered by the investigator to be in good general health as determined by medical history.
4. Female subjects must be non-pregnant and non-lactating and meet one of the following criteria: a) post-menopausal (defined as 12 consecutive months with no menses without an

alternative medical cause or documented plasma follicle-stimulating hormone level in the post-menopausal range); b) surgically sterile (ie, hysterectomy, bilateral tubal ligation, or bilateral oophorectomy). NOTE: these procedures and laboratory test results must be confirmed by physical examination or official written confirmation of a procedure; c) if of childbearing potential (defined as any female who has experienced menarche and who is NOT permanently sterile or post-menopausal), agrees to be heterosexually inactive from at least 21 days prior to enrollment and through 3 months after the final vaccination or agrees to consistently use any of the following methods of contraception from at least 21 days prior to enrollment and through 3 months after the final vaccination: condoms (male or female) with spermicide, diaphragm with spermicide, cervical cap with spermicide, intrauterine device, oral or patch contraceptives, Norplant®, Depo-Provera®, or other FDA-approved contraceptive method that is designed to protect against pregnancy. Periodic abstinence (eg, calendar, ovulation, symptothermal, post-ovulation methods) and withdrawal are not acceptable methods of contraception. Male subjects must use an acceptable method of birth control (see above) and must also agree to refrain from donation of sperm from the time of first vaccination until 3 months following the last vaccination. Periodic abstinence, declaration of abstinence for the duration of the study, and withdrawal are not acceptable methods of contraception.

5. Subject assigned to the flavivirus-seropositive group has received a yellow fever vaccination in the past 20 years by either: a) military assignment in the previous 20 years that requires a yellow fever vaccination; or 2) yellow fever vaccination documented on an international certificate or other confirmatory documentation.
6. The subject understands and agrees to comply with the study procedures and provides written informed consent.
7. The subject has access to a consistent and reliable means of telephone contact, which may be in the home, workplace, or by personal mobile electronic device.
8. The subject agrees to stay in contact with the study site for the duration of the study, to provide updated contact information as necessary, and has no current plans to move from the study area for the duration of the study.

### **3.2.2 Exclusion Criteria**

Subjects meeting any of the following criteria will be excluded from the study:

1. The subject has any ongoing significant chronic illness requiring medical or surgical care. Asymptomatic conditions or findings (eg, mild hypertension, dyslipidemia) that are not associated with evidence of end-organ damage are not exclusionary provided that they are being appropriately managed and are clinically stable in the opinion of the investigator (ie, unlikely to result in symptomatic illness within the time-course of this study).
2. The subject has a history of active cancer (malignancy) in the last 10 years (exception is subjects with adequately treated non-melanomatous skin carcinoma, who may participate in the study).
3. The subject is a female of childbearing potential and has a positive pregnancy test at Screening or on the day of vaccination.
4. The subject has abnormal liver enzyme tests (increase in aspartate aminotransferase, alanine aminotransferase, or alkaline phosphatase) at Screening.
5. The subject has received another investigational product in another investigational study within 60 days, or 5 half-lives, whichever is longer, before the planned date of first vaccination.
6. The subject has received any live attenuated vaccines within 4 weeks before enrollment or inactive vaccines within 2 weeks before enrollment, or plans to receive any vaccine during the active vaccination period (through 4 weeks after their last planned vaccination).
7. The subject has received (at any time) a vaccine for Zika or dengue vaccine.
8. The subject has a history of confirmed Zika or dengue infection.
9. The subject has lived in or visited any Zika-endemic area (as defined by WHO; [Appendix 4](#)) greater than 4 weeks in duration (flavivirus-seronegative group, only).
10. The subject has received any vaccination for a flavivirus (eg, yellow fever, Japanese encephalitis) in his or her lifetime (flavivirus-seronegative group, only), or received a vaccination for a flavivirus more than 20 years ago (flavivirus-seropositive group, only).

11. The subject has a positive West Nile virus antibody titer above the detection level of the assay (flavivirus-seronegative group, only). NOTE: West Nile virus titers are considered valid for a period of 90 days (allowing for the screening period on West Nile virus to exceed the standard 28 days as noted for all other screening parameters).
12. The subject has reported previously participating in an investigational study involving LNPs.
13. The subject has a history of hypersensitivity or serious reactions (eg, anaphylaxis, urticaria, other significant reaction) to previous vaccinations.
14. The subject has any known or suspected autoimmune disease or immunosuppressive condition, acquired or congenital, as determined by medical history and/or physical examination.
15. The subject has a history of inflammatory arthritis.
16. The subject has a neurologic disorder (eg, history of seizures, Guillain-Barré syndrome, dementia, vasculitis, or any known congenital or acquired disorder).
17. The subject has a history of febrile disease with arthritis or arthralgia within 2 weeks of dose administration.
18. The subject received immunoglobulins and/or any blood products within the 3 months preceding the administration of the study drug or plans to receive such products at any time during the study.
19. The subject has had chronic administration (defined as more than 14 continuous days) of an immunosuppressant or other immune-modifying drug within 6 months before vaccine administration or plans to receive any products during the active vaccination period (through 4 weeks after their last planned vaccination). An immunosuppressant dose of a glucocorticoid will be defined as a systemic dose of  $\geq 10$  mg of prednisone per day or equivalent. The use of topical, inhaled, and nasal glucocorticoids will be permitted.
20. The subject has any acute illness at the time of enrollment (defined as the presence of a moderate or severe illness with or without fever, or an oral body temperature  $>37.9^{\circ}\text{C}$  on the planned day of vaccination). In such cases, subjects may be re-evaluated during the

screening period for resolution of the illness to allow at least 3 days of wellness before the planned vaccination as long as they remain within the 28-day screening period.

21. The subject has any significant disorder of coagulation (acquired or hereditary) requiring ongoing or intermittent treatment. Subjects receiving prophylactic antiplatelet medications, eg, low dose acetylsalicylic acid ( $\leq 100$  mg/day or equivalent), and without clinically apparent bleeding tendency, are eligible.
22. The subject has a history of idiopathic urticaria.
23. The subject has a documented history of alcohol abuse or drug addiction within 1 year before the planned day of dose administration.
24. The subject has a positive test result for drugs of abuse at Screening or on the day of first vaccination.
25. The subject has any abnormality or permanent body art (eg, tattoo) that, in the opinion of the investigator, would obstruct the ability to observe local reactions at the injection site (deltoid region).
26. The subject has any condition that, in the opinion of the investigator, would pose a health risk to the subject if enrolled or could interfere with evaluation of the study drug or interpretation of study results (including neurologic or psychiatric conditions deemed likely to impair the quality of safety reporting).
27. The subject has a positive test result for hepatitis B surface antigen, hepatitis C virus antibody, or human immunodeficiency virus types 1 or 2 antibodies.
28. The subject has donated blood or blood products  $>450$  mL within 30 days of dosing.
29. The subject has screening safety laboratory test results (urine and serum) outside the normal range of the laboratory and with a toxicity score with Grade 1 or higher.
30. The subject has screening vital sign of blood pressure, heart rate, or respiratory rate that is equal to or greater than Grade 1 by toxicity score.
31. The subject is an employee or first degree relative of the Sponsor, PPD, or study site personnel.

Note that some exclusion criteria are time-related. A subject may be re-evaluated on more than one occasion during the screening period to assess for resolution. There is allowance to repeat an abnormal vital sign measurement and Grade 1 laboratory abnormalities (except aspartate aminotransferase, alanine aminotransferase, and alkaline phosphatase) once to allow for inclusion into the study and the last value measured will be used to allow inclusion in the study.

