8. The subject agrees to stay in contact with the study site for the duration of the study, to provide updated contact information as necessary, and has no current plans to move from the study area for the duration of the study.

**Exclusion criteria:** Subjects meeting any of the following criteria will be excluded from the study:

1. The subject has any ongoing significant chronic illness requiring medical or surgical care. Asymptomatic conditions or findings (eg, mild hypertension, dyslipidemia) that are not associated with evidence of end-organ damage are not exclusionary provided that they are being appropriately managed and are clinically stable in the opinion of the investigator (ie, unlikely to result in symptomatic illness within the time-course of this study).
2. The subject has a history of active cancer (malignancy) in the last 10 years (exception is subjects with adequately treated non-melanomatous skin carcinoma, who may participate in the study).
3. The subject is a female of childbearing potential and has a positive pregnancy test at Screening or on the day of vaccination.
4. The subject has abnormal liver enzyme tests (increase in aspartate aminotransferase, alanine aminotransferase, or alkaline phosphatase) at Screening.
5. The subject has received another investigational product in another investigational study within 60 days, or 5 half-lives, whichever is longer, before the planned date of first vaccination.
6. The subject has received any live attenuated vaccines within 4 weeks before enrollment or inactive vaccines within 2 weeks before enrollment, or plans to receive any vaccine during the active vaccination period (through 4 weeks after their last planned vaccination).

7. The subject has received (at any time) a vaccine for Zika or dengue vaccine.
8. The subject has a history of confirmed Zika or dengue infection.
9. The subject has lived in or visited any Zika-endemic area (as defined by the World Health Organization [WHO; [Appendix 4](#)]) greater than 4 weeks in duration (flavivirus-seronegative group, only).
10. The subject has received any vaccination for a flavivirus (eg, yellow fever, Japanese encephalitis) in his or her lifetime (flavivirus-seronegative group, only), or received a vaccination for a flavivirus more than 20 years ago (flavivirus-seropositive group, only).
11. The subject has a positive West Nile virus antibody titer above the detection level of the assay (flavivirus-seronegative group, only).  

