## 6.4 Appendix 4: World Health Organization Zika Situation Report as of February 2017

Figure 2. New detection of mosquito-borne Zika virus infections, January 2013–February 2017

The WHO map (dated 01 February 2017; [WHO 2017](#)) showing Zika-endemic regions is subject to routine updating. The most up-to-date regions can be found within each situation report, including the countries and territories listing Zika virus transmission (WHO Table 1 below; [WHO 2017](#)) at: <http://www.who.int/emergencies/zika-virus/situation-report/en/>

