**Table 1. Countries and territories that have reported mosquito-borne Zika virus transmission**

Classification	WHO Regional Office	Country / territory	Total
Category 1: Countries with a reported outbreak from 2015 onwards #	AFRO	Angola; Cabo Verde; Guinea-Bissau	3
	AMRO/PAHO	Anguilla; Antigua and Barbuda; Argentina; Aruba; Bahamas; Barbados; Belize; Bolivia (Plurinational State of); Bonaire, Sint Eustatius and Saba – Netherlands; Brazil; British Virgin Islands; Cayman Islands; Colombia; Costa Rica; Cuba; Curaçao; Dominica; Dominican Republic; Ecuador; El Salvador; French Guiana; Grenada; Guadeloupe; Guatemala; Guyana; Haiti; Honduras; Jamaica; Martinique; Mexico; Montserrat; Nicaragua; Panama; Paraguay; Peru; Puerto Rico; Saint Barthélemy; Saint Kitts and Nevis; Saint Lucia; Saint Martin; Saint Vincent and the Grenadines; Sint Maarten; Suriname; Trinidad and Tobago; Turks and Caicos; United States of America; United States Virgin Islands; Venezuela (Bolivarian Republic of)	48
	WPRO	American Samoa; Fiji; Marshall Islands; Micronesia (Federated States of); Palau; Samoa; Singapore; Tonga	8
Subtotal			59
Category 2: Countries with possible endemic transmission or evidence of local mosquito-borne Zika infections in 2016 or 2017	SEARO	Indonesia; Maldives; Thailand	3
	WPRO	Malaysia; New Caledonia; Philippines; Viet Nam	4
Subtotal			7
Category 3: Countries with evidence of local mosquito-borne Zika infections in or before 2015, but without documentation of cases in 2016 or 2017, or outbreak terminated	AFRO	Gabon**	1
	PAHO/AMRO	ISLA DE PASCUA – Chile**	1
	SEARO	Bangladesh**	1
	WPRO	Cambodia**; Cook Islands**; French Polynesia**; Lao People's Democratic Republic; Papua New Guinea; Solomon Islands; Vanuatu	7
Subtotal			10
Total			76

PPD will operationalize the monitoring of the Zika-endemic changes and notify a site if they appear to be reaching the endemic listing.

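### Does exclusion criterion 9, read with Appendix 4, bar ordinary US residents from the seronegative group?

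*Protocol*

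**What the plan says.** Criterion 9 in section 3.2.2 excludes from the seronegative group only a subject who has "lived in or visited any Zika-endemic area (as defined by WHO", Appendix 4 being cited, for longer than 4 weeks. The Protocol Synopsis repeats the rule: "lived in or visited any Zika-endemic area (as defined by the World Health Organization".

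Appendix 4 (section 6.4) offers three things to consult:

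- a dated WHO map, described as "showing Zika-endemic regions is subject to routine updating";
- the WHO situation reports: "The most up-to-date regions can be found within each situation report, including the countries and territories listing Zika virus transmission";
- a printed Table 1, whose title speaks of places that have reported mosquito-borne transmission.

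Table 1 has three categories. Category 1 is headed "Countries with a reported outbreak from 2015 onwards" and its Americas row includes "United States of America; United States Virgin Islands; Venezuela (Bolivarian Republic of". Puerto Rico stands in the same row, and American Samoa in the Western Pacific row of Category 1. Category 2 is headed "Countries with possible endemic transmission or evidence of local mosquito-borne Zika infections in 2016 or 2017". The appendix closes by assigning someone to follow changes in the listing and to alert a site that seems to be approaching it.

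The Synopsis title places the trial in a region that is not Zika-endemic, and section 3.2 places the sites in the United States or its territories.

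**The concern.** The criterion borrows its definition wholly from Appendix 4, and the only list printed there contains the country in which the trial recruits. Anyone who took Table 1 as the definition, at country level, would find every long-term US resident ineligible for the seronegative group. Nothing in the readable text says whether the map or the table decides, which categories count, or whether an area is a country, a territory or something smaller.

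Two consequences could follow. Section 5.2.2 counts departures from exclusion criteria among possible protocol violations, and section 3.6.4 keeps subjects with major violations out of the Per-Protocol set, so an auditor reading literally could question a large share of the trial. There is also a scientific side. Section 1.1 says most Zika infections are asymptomatic or mild, so criterion 8, which needs a confirmed infection, will miss some, and criterion 9 is the only criterion based on geographic Zika exposure.

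**Working it through.** **Recount of Table 1 (section 6.4).**

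- Category 1: 3 + 48 + 8 = 59, as printed.
- Category 2: 3 + 4 = 7, as printed.
- Category 3: 1 + 1 + 1 + 7 = 10, as printed.
- Total: 59 + 7 + 10 = 76, as printed.
- US or US-territory entries: 3 in the Americas row (United States of America, Puerto Rico, US Virgin Islands) + 1 in the Western Pacific row (American Samoa) = 4. All 4 are in Category 1.

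**What a literal country-level reading would do.** Planned size is 3 cohorts × 30 = 90 (sections 3.1 and 3.6.3). About two-thirds are to be flavivirus-naïve (section 3.4.1): 2/3 × 90 = 60, or 20 per cohort. The sentinel subjects, 3 × 3 = 9, are all seronegative (section 3.1). Essentially all of these would be barred, and the seronegative part of the trial could not be enrolled. A reading with that result is a reason to look again at the text.

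**The passages side by side.**

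1. *Which item matches the criterion's term.* The criterion turns on an endemic *area*. In Appendix 4 the item described in those terms is the map. Table 1 has a different title: reported transmission.
2. *Geographic level.* The criterion says area, and Appendix 4 says regions where it describes the map and its updates. The closing line alerts a *site* that is approaching the listing. If the whole country counted as one endemic unit, every mainland site would already be listed and that line would have no purpose.
3. *Title and sites.* A trial in a non-endemic region with US sites is coherent only if the US is not one endemic area.
4. *Conduct so far.* Section 1.5 reports antibody results from seronegative subjects in Cohort 2. This shows at most that a whole-country bar was not enforced. It does not show how criterion 9 was applied in detail.
5. *A Category 2-only reading.* That is the only heading containing the word endemic (7 entries, none of them US). But it would make Brazil and all the other reported-outbreak countries non-endemic on the strength of one word, so it is not a serious rival.
6. *The three territories.* They are named as separate entries, so the whole-country difficulty does not arise for them. Section 3.2 allows sites there and requires none, and criterion 9 does not bind the seropositive group. A territory site that recruited only seropositive subjects would contradict nothing.

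**Effect on interpretation if an exposed subject slipped in.** Criterion 11 excludes a positive West Nile titer from the seronegative group, and section 1.6 relies on that test's cross-reactivity with other flaviviruses. The seroconversion definition in section 3.6.5.1 depends on baseline Zika PRNT50: below 1:10 a subject needs at least 1:20 afterwards, and from 1:10 upward a 4-fold rise. Prior exposure that shows at baseline is therefore allowed for in that endpoint.

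**The case for a change.** The best case for a change is that it costs one sentence and would remove a real looseness. Appendix 4 does refer to Table 1 as part of the situation report in which up-to-date regions are found, so the table cannot be dismissed as background. Common sense settles the mainland, but it does not tell a site in Puerto Rico whether map or table decides, nor what to do with Category 3 places where transmission has ended. Baseline PRNT50 is drawn on the day of first vaccination and is not an eligibility test, so criterion 9 carries some weight of its own.

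Part of this stands. The readable text does not name the governing item, and citing it would do no harm. Two things count against treating it as a defect. The map, and the note belonging to the marker on the Category 1 heading, could not be read in the copy used here. Either may already give the limit, and their absence from that copy is no fault of the protocol. Also, the territory question is a matter of applying a list in which those places appear by name, and no two statements in the protocol collide over it.

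**Conclusion.** No change follows. This is a missing detail that sites fill sensibly: the wording of the criterion, the site-level monitoring line, the title and the site statement all point to a local reading of endemic area. Writing that down would record the evident intent and alter no screening procedure, since residence and travel history are already needed.

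The shown effect is nil. No ineligible subject, no loss from an analysis set and no altered estimate can be demonstrated. The figure of about 60 subjects belongs only to a reading that the protocol itself rules out.

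The conclusion assumes that sites apply the criterion locally and that the map and the Category 1 note do not say otherwise. If the map marked the entire United States as endemic, title and criterion would truly clash. Nothing readable suggests that, and the closing line of Appendix 4 speaks against it.
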